**4.9. Withdrawal from the study/discontinuation of participants**

Patients can withdraw from the study at any time without explanation. The investigators will try to collate and analyze clinical data at the time of withdrawal. Patients who withdraw will not be replaced, and investigators will continue to record their survival and test tissue samples obtained prior to withdrawal. Patients who complete an investigational drug-related AE assessment prior to withdrawal from the study will be included in the safety assessment of Ad-TD-nsIL12 as a valid case.

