### 4.3. In-hospital period

- After stereotactic biopsy, the Ommaya reservoir will be inserted through the biopsy channel and a single injection of Ad-TD-nsIL12 will be delivered immediately after surgery.
- The injection dose start with  $3 \times 10^9$ vp (D1) and follow  $1 \times 10^{10}$ vp (D2),  $3 \times 10^{10}$ vp (D3) for climbing. If 2 or 3 patients develop severe adverse event (SAE) according to NCI-CTCAE at D1. The dose will then be reduced to  $1 \times 10^9$ vp (D0). If one patient develops SAE at the D1 dose, the other 3 patients will continue to be included with the D1 dose to assess whether the occurrence of this SAE is accidental. If SAE develops in 1 of the next 3 patients, following patients will receive the D0 dose.
- Before subsequent patients enrollment, the former patient in each cohort must be observed for at least 6 days after virus injection. The administration of virus to participants in the new cohort will be at least 10 days behind the last participant in the previous cohort.
- If the patient presents with symptoms of decreased brain function or decreased cardiovascular perfusion, or if there is an allergic reaction or signs of anaphylaxis, administration of Ad-TD-nsIL12 should be discontinued. In addition, treatment of Ad-TD-nsIL12 will also be interrupted if other AEs deemed necessary by investigators to be interrupted. In addition, if ventricular penetration is considered to have occurred during viral use, the dosing procedure will be terminated and no further treatment with Ad-TD-nsIL12 will be given, and such patients will be observed and examined by virologic testing (AdV) and further follow-up.
- The tumor tissue obtained at the time of biopsy or excision, as well as the collected blood samples, will be archived in our hospital for future analysis.
- Visit 0:  $3 \pm 1$  days after Ad-TD-nsIL12 injection. Including:
  - Physical examination, including vital signs, weight, and height;
  - Neurological examination and functional status assessment (LPS or KPS), life quality assessment;
  - Blood tests, blood biochemistry (containing C-reactive protein), coagulation function assessment and other blood tests (including detection of adenovirus antigens and anti-adenovirus antibodies in serum);
  - MRI (with or without gadolinium) and tumor response assessment;
  - Assessment and documentation of adverse events, including concomitant medications, including steroids.

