#### **4.8. Dose escalation and determination of the maximum tolerated dose**

**(MTD).**

- The dose will start with  $3 \times 10^9$ vp. Three dose stages are planned:  $3 \times 10^9$ vp,  $1 \times 10^{10}$ vp as well  $3 \times 10^{10}$ vp.
- Each cohort will include 3 to 6 participants depending on the occurrence of AE. The criteria for dose climbing are as follows:
  - If there were no Ad-TD-nsIL12 related SAEs (NCI-CTCAE  $\geq$  grade 3) occurred within 6 days after virus injection in the previous patient in the same cohort, the latter patient continues to be included.
  - If 1 patient developed Ad-TD-nsIL12 related SAE in a cohort, 3 patients will continue to be included in this cohort to verify whether it's accidental, and if any 1 of the subsequent 3 patients developed Ad-TD-nsIL12 related SAE, it would be considered as the dose limiting toxicity (DLT), and the previous dose is taken as the maximum tolerated dose (MTD).
  - If 2 patients in the same cohort developed investigational drug-related SAE, it will be considered to be DLT, then the trial will be terminated and the dose used in previous cohort will be defined as MTD.
  - If all 3 patients in the same cohort had no drug-related SAE within 10 days after virus injection, the dose would be upgraded to the next cohort.
  - If DLT presented in the first cohort (D1), dose adjustment will be made according to what is described in protocol 4.3, and if DLT still occurs at D0, the trial terminates.
  - If DLT still does not occur at the highest dose D3, MTD is not defined and the trial terminates.
- Any clinical SAEs deemed to be likely to be associated with Ad-TD-nsIL12 will be recorded by the investigator and graded accordingly. Follow-up will continue until the SAE disappears or drops to grade 1.
- In addition, if non-neurological complications related to any surgical or anesthesia management occur (including, but not limited to, respiratory failure, pneumonia and other systemic infections, cardiac arrest, myocardial infarction, pulmonary embolism, deep vein thrombosis, tracheal and laryngeal trauma, postanesthesia lethargy, fatigue, and short-term memory loss), dose reduction may be considered after discussion with the principal investigator.

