### **10.2. Estimation of sample size**

Sample size was determined by the incidence of DLT in three dosing cohorts, each with 3 to 6 assessable participants. If DLT is not observed, at least nine participants will be included if MTD is not reached. Admission to nine participants was expected to take 10

to 12 months; 18 patients about 15-20 months.

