### **10.3.Safety**

Patients who do not complete the study, for any reason, will include all available data prior to termination of the study in the safety analysis. AEs will be summarized by population and dose group, and tabulated by severity, relationship with Ad-TD-nsIL12, and causation. In addition, SAEs, AEs that may be related to Ad-TD-nsIL12, and AEs that are not related to Ad-TD-nsIL12 will be aggregated separately. Concurrent conditions will be listed and may be identified as possible confounding factors in the treatment-response relationship. Follow-up and treatment for AE will also be documented. Summary data includes univariate statistics for mean, standard error, percentage, and median. AE-related clinical laboratory results will provide descriptive statistics on selected laboratory parameters based on population, patients, study dates, and dose groups.

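### Section 4.9 bars replacement of withdrawn patients, while the 3+3 rule and sample size need three to six assessable patients per cohort; one loss before day 10 leaves the dose decision undefined

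*Protocol*

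**What the plan says.** - **Replacement (Protocol 4.9).** The rule is flat: "Patients who withdraw will not be replaced, and investigators will continue to record their survival". It does not distinguish withdrawal before the dose decision from withdrawal after it.
- **Sample size (10.2).** "Sample size was determined by the incidence of DLT in three dosing cohorts, each with 3 to 6 assessable participants". If no DLT is seen, "at least nine participants will be included if MTD is not reached". Section 1.6 gives the total as 9 to 18. The word assessable is not defined anywhere in the protocol.
- **Escalation (4.8).** "Each cohort will include 3 to 6 participants depending on the occurrence of AE". The dose goes up when all three patients in a cohort are free of drug-related SAEs for 10 days. One such event adds three more patients. When a dose is judged to cause DLT, the previous dose becomes the MTD.
- **Withdrawn patients in the safety evaluation.** Section 4.9: "Patients who complete an investigational drug-related AE assessment prior to withdrawal from the study will be included in the safety assessment", as a valid case. No time is given by which that assessment must be complete. Section 10.3: "Patients who do not complete the study, for any reason, will include all available data prior to termination of the study in the safety analysis".
- **Visits (4.3, 4.4).** Adverse events are assessed at Visit 0, 3±1 days after injection. The next planned visit is at 28±5 days. No visit falls at day 10.

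**The concern.** A 3+3 decision draws all its evidence from three or six patients, each watched for the full window. Section 10.2 recognises this by counting assessable participants. Section 4.9 removes the means of keeping that number: once a patient leaves early, the cohort stays one short, and no section says what then follows. The rule governs enrolment and escalation while the trial is running, so it cannot be left to a later analysis document.

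The primary endpoint, the MTD, is at stake. Section 4.8 names the previous dose as MTD without requiring more patients at that dose, so a dose passed on too little follow-up gets no second look.

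**Working it through.** **1. The plan's own figure.** Three cohorts × 3 = 9 and three cohorts × 6 = 18, which match sections 10.2 and 1.6 exactly. The figures contain no allowance for loss. With no replacement, one early loss in the nine-patient case leaves 9 − 1 = 8 assessable.

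**2. What 4.8 does with a cohort of two observed patients.**
- Strict reading: the condition of three patients free of events for 10 days is not met, so the dose cannot go up. Section 4.9 forbids a replacement, and with no event there is no expansion. The cohort has no defined next step.
- Loose reading: a child assessed at Visit 0 (day 2 to 4) who withdraws on day 5 has completed an adverse-event assessment, so can be called a valid case under 4.9 with no SAE recorded. The three are then complete on paper, although only two were observed to day 10.

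**3. Size under the loose reading, given one loss.** Let p be the true DLT rate.
- Chance of no observed event = (1 − p)^n. At p = 0.33: 0.67² = 0.449 against 0.67³ = 0.301. At p = 0.40: 0.360 against 0.216. At p = 0.50: 0.250 against 0.125.
- Chance of clearing with the expansion step = (1 − p)^n1 + n1·p·(1 − p)^(n1−1)·(1 − p)^n2, with n1 and n2 the observed patients in the first and second three. At p = 0.33, two then three: 0.449 + 2 × 0.33 × 0.67 × 0.301 = 0.582. Three then three: 0.301 + 3 × 0.33 × 0.449 × 0.301 = 0.434.
- One-sided 95% upper bound on p after no events = 1 − 0.05^(1/n): 77.6% after 0/2, 63.2% after 0/3.

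**4. How often a loss would occur.** The protocol states no early-withdrawal rate, so d is an assumption. P(at least one loss) = 1 − (1 − d)^n.

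| Assumed d | In a cohort of 3 | Among 9 patients |
|---|---|---|
| 1% | 3.0% | 8.6% |
| 2% | 5.9% | 16.6% |
| 5% | 14.3% | 37.0% |
| 10% | 27.1% | 61.3% |

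**5. Size not conditional on a loss.** Suppose every early withdrawal counts as event-free and loss is independent of toxicity. Then P(no observed event in three) = (1 − p(1 − d))³. At p = 0.33:
- d = 0: 0.670³ = 0.301
- d = 1%: 0.6733³ = 0.305
- d = 5%: 0.6865³ = 0.324
- d = 10%: 0.703³ = 0.347

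The rise is about 0.4, 2.3 and 4.7 percentage points.

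**The case against.** The best defence is that the exposed period is short. There is one injection, given straight after surgery, and then 10 days. Withdrawal in that time may be rare, and 4.9 keeps patients whose assessment was completed first. Section 4.8 also asks for all three patients, which on its plain words stops escalation on two. This stands as a limit on size. It does not remove the defect, because the strict reading leaves the cohort stuck and the valid-case wording, having no time point, leaves the loose reading open.

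A reader might infer more, and the documents do not support it:
- **That missing follow-up always favours escalation.** It does not under the strict reading, and no section says that unobserved time counts as event-free.
- **That a partly dosed child counts at the nominal dose.** Section 4.3 says that on suspected ventricular penetration "the dosing procedure will be terminated and no further treatment with Ad-TD-nsIL12 will be given" and that such patients are followed further. The protocol is silent on how they count for the dose decision, and they have not withdrawn, so 4.9 does not by its terms apply to them.
- **That 4.9 and 10.3 set up two safety populations.** Section 4.9 says that patients with a completed assessment are included. It does not say that others are excluded, so the two sections can be read together.

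**Conclusion.** The conflict is real. A stated rule in 4.9 defeats the assessable cohort size on which 10.2 rests and which the escalation step in 4.8 needs, and no other section repairs it. After one loss before day 10, the cohort either stalls or can be cleared on two observed patients.

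It would be tempting to quote the gap of about 15 points (0.449 against 0.301 at a true rate of 33%) as the trial's error. It applies only after a loss has occurred and only on the loose reading. Averaged over assumed loss rates of 1% to 10%, the rise is about 0.4 to 4.7 points, again on the loose reading and with loss independent of toxicity. The case for change therefore does not depend on a large average effect. It rests on the primary-endpoint rule having no defined outcome in a foreseeable situation that a few words would settle.

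**What to change.** 1. Define assessable for DLT as followed through the window in 4.8, or having had a DLT.
2. Amend 4.9 so that a patient who withdraws before that point without a DLT is replaced at the same dose level for the dose decision. A patient with a DLT always counts and is not replaced.
3. State the 9 to 18 in section 1.6 as assessable patients.

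Two clarifications belong in the same amendment, though neither is a shown error: say whether a patient whose injection was stopped under 4.3 is assessable for the dose decision, and say that the valid-case wording in 4.9 does not narrow the safety analysis in 10.3.

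The cost is a wording amendment and an occasional extra enrolled patient. Enrolled number = assessable number / (1 − d). At an assumed 10% early loss, 9/0.9 = 10 and 18/0.9 = 20. At 1% to 5%, rounding up gives about 10 to 19. The assessable total stays at the 9 to 18 already planned.

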**4.10. Duration of participation of each patient**

Each patient will receive viral injections prior to any other oncology treatment and will undergo clinical and radiological follow-up within 3 months after Ad-TD-nsIL12 treatment. Then, patients will continue to be followed up until two years. The research team will contact each patient by phone or mail at 6, 12, 18 and 24 months to update clinical information. Patients will continue to receive follow-up until five years if they are still alive at 24 months after viral treatment. At any time, patients can freely withdraw.

**5. Experimental drug****5.1. Drug introduction**

Ad-TD-nsIL12 is an adenovirus that makes the virus replicate only in tumor cells by deleting E1A-CR2, enhancing targeting and reducing toxicity to normal cells. Deletion of E1B-19K accelerates apoptosis of infected tumor cells and enhances the ability to kill tumor cells. Deletion of E3-gp19K is beneficial to tumor-specific antigen presentation in cells and enhances anti-tumor effect. Retain E1B-55K to ensure the replication ability of the virus and improve the tumor killing ability. Preserves E3B, inhibits macrophage-mediated viral clearance, improves antitumor effect. In addition, IL-12 is introduced into Ad-TD to realize tumor immunogene therapy and further improve the effect of tumor treatment. After modification, the appropriate level of IL-12 in the blood can be maintained, so that the systemic anti-tumor effect of IL-12 is stronger, and the side effects of high concentrations of IL-12 in the blood are also avoided.

## **5.2. Formulation and storage**

**Formulation:** The final Ad-TD-nsIL12 product is BioTTT001, formulated with a special virus protection solution. The concentration of reagents was  $5 \times 10^{11}$  vp/mL at 1 mL each. **Storage:** Ad-TD-nsIL12 vials should be stored in the research pharmacy freezer at  $\leq -80^{\circ}\text{C}$  prior to dilution. The diluent should be kept at room temperature. All research supplies will be kept in a properly locked room where only pharmacy staff will be allowed to enter and the temperature of the freezer must be monitored regularly.

## **5.3. Stability testing**

Ad-TD-nsIL12 has passed the stability test of biological products, which has good stability and a shelf life of up to two years. Stability-tested properties of final biologics include appearance, potency (viral titer, viral particle concentration, vp/IU ratio), and safety. Virus appearance, titer, viral particle concentration, and vp/IU ratio were detected at 0, 3, 6, 12, 24, and 36 months time points. The products of the three batches of pilot continuous production are all qualified and stable.

## **5.4. Production establishment**

It is entrusted by Beijing Hammer Biotechnology Co., Ltd. to Shenzhen Yuanxing Gene Technology Co., Ltd. to produce.

## **5.5. Handlers**

The handling and preparation of Ad-TD-nsIL12 will follow the institutional standards for biosafety secondary reagents as specified in the Hazards and Biosafety Manual and Biosafety in Microbiology and Biomedical Laboratories. In addition, standard chemotherapy preparation precautions (gowns, gloves, masks, and glasses) and aseptic techniques will be followed when preparing the required dose of Ad-TD-nsIL12. Only needle-locked syringes or disposable syringes are used to inject or inhale biohazardous liquids. Caution should be used when handling needles and syringes to avoid self-spraying and aerosol generation during use and disposal. The original Ad-TD-nsIL12 vial and all syringes, needles, and needle caps that come into contact with Ad-TD-nsIL12 should be placed in a disinfectant cup after the procedure.

# **6. Response assessment**

## **6.1. Primary assessment**

- Adverse events (according to NCI-CTCAE v 5.0)
- Neurological examination
- LPS or KPS score
- Laboratory test results
- Use of concomitant drugs

## **6.2. Secondary assessment**

- Efficacy will be assessed based on survival and tumor response as determined by

RAPNO criteria. Time to disease progression, 6-month progression-free survival, median progression-free survival, 12-month overall survival (OS12), and median overall survival will also be determined. Quality of Life Assessment (PedsQL™). Ad-TD-nsIL12-induced immune response.

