#### 4.4. Follow-up period

- After enrollment, clinical follow-up will be conducted every 4 weeks for the first 3 months after viral treatment. After 3 months, follow-up visits can be performed by phone, images and blood tests results can be sent by email, or patients can come to our hospital for treatment and follow-up if they wish. Treatment tolerability was measured by severity classification of adverse events (NCI-CTCAE V5.0) and correlation with the investigating drug.
- Visit 1: 28±5 days after Ad-TD-nsIL12 injection. Including:
  - Physical examination, including vital signs, weight, and height.
  - Neurological examination and functional status assessment (LPS or KPS);
  - Quality of Life Assessment (PedsQL™);
  - Laboratory blood tests, some of which will be retained for subsequent analysis;
  - MRI (with or without gadolinium) and tumor response assessment;
  - Evaluation and documentation of adverse events, concomitant medications;
  - Steroid evaluation.
- Visit 2: 8±1 weeks after Ad-TD-nsIL12 injection. Including:
  - Physical examination, including vital signs, weight, and height.
  - Neurological examination and functional status assessment (LPS or KPS);
  - Quality of Life Assessment (PedsQL™);
  - Laboratory blood tests, some of which will be retained for subsequent analysis;
  - MRI (with or without gadolinium) and tumor response assessment;
  - Evaluation and documentation of adverse events, concomitant medications;
  - Steroid evaluation.
- Visit 3: 12±1 weeks after Ad-TD-nsIL12 injection. Including:
  - Physical examination, including vital signs, weight, and height.
  - Neurological examination and functional status assessment (LPS or KPS);
  - Quality of Life Assessment (PedsQL™);
  - Laboratory blood tests, some of which will be retained for subsequent analysis;
  - MRI (with or without gadolinium) and tumor response assessment;
  - Evaluation and documentation of adverse events, concomitant medications;
  - Steroid evaluation.
- Visit 3 is the last designated clinical follow-up, after which the patient's overall AE will be concluded and assessed.
- Except for the 3 planned visits, both patients and investigators may request unplanned follow-up at any time.
- During follow-up, if viral infection of CSF is suspected, the investigator will decide whether to perform virological (AdV) testing.

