#### 4.5. Remote follow-up

- Remote follow-up contact: (6 months ± 1 month, 12 months ± 1 month, 18 months ± 1 month, 24 months ± 1 month)
- Visit :
  - Survival;
  - Assessment of quality of life;

- Evaluation and documentation of adverse events, concomitant medications;
- Steroid use;
- If any imaging tests are performed, radiological information is collected and analyzed.
- After that, patients will continue to receive standardized treatment for DIPG, and investigators will continue to follow up on their basic information, including but not limited to survival, quality of life, and occurrence of AE. Depending on the special and necessary clinical situation, the investigator may request increased follow-up frequency, or even follow-up in Sanbo Brain Hospital.
- At the time of tumor progression, the study will end, the patient and their guardians could chose following treatment, and the investigators will continue to collect basic information about clinical status (including at least survival and quality of life assessment) until the patient dies or at least 2 years after virus injection.
- If the tumor does not progress, the investigators will continue to collect basic information about clinical status (including at least survival and quality of life assessment) until the patient dies or at least 5 years after virus injection. Again, researchers can decide to conduct a final analysis of the study data or to continue long-term follow-up of certain patients at any time, this decision that can only be made after all patients have died or been followed for more than 1 year.

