#### **4.7. Radiological follow-up**

- MRI will be used to evaluate tumor response, and assessment of tumor reflection requires a uniform sequence from baseline (T2 or enhanced phase recommended).
- Time point
  - Within 15 days before Ad-TD-nsIL12 injection (baseline);
  - Within 3 days after Ad-TD-nsIL12 injection;
  - Visit 1 (28±5 days after Ad-TD-nsIL12 injection);
  - Visit 2 (8±1 weeks after Ad-TD-nsIL12 injection);
  - Visit 3 (12±1 weeks after Ad-TD-nsIL12 injection).
- The RAPNO criteria (2020) will be used to assess tumor response. If a pseudoprogression is suspected according to image changes within the first two months after viral injection, the final verdict will be made by a radiologist based on the advanced MRI sequence. After the final planned MRI is completed (Visti 3), the study procedure will be completed, after which the patient will continue to receive standardized treatment, and the investigator will continue to follow up with basic information, including but not limited to survival, quality of life, and occurrence of AE.
- Researchers can request an MRI at any time during the study to determine the imaging response of the tumor.

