## **10. Statistical methods**

### **10.1. Study endpoints**

- Primary endpoint  
The maximum tolerated dose (MTD) of Ad-TD-nsIL12. (According to the criteria of NCI-CTCAE V5.0, MTD will be defined as doses below the dose that causes DLT. If no DLT has occurred at D3, the trial is terminated and MTD is not defined.)
- Secondary endpoints  
Tumor response based on tumor size change on continuous MRI scans after injection, time to progression, viral activity based on sample analysis, and immunogenicity based on adenovirus antibodies in serum. Overall survival of the patient. Due to the small number of participants, it is expected that the secondary endpoint will only be used to provide reference trends for future phase II efficacy studies.

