### **10.4.Effectiveness**

In this study, tumor response will be assessed according to RAPNO criteria. Response to treatment will be determined by the size of the brain tumor from baseline, at 28 days, 8 weeks, and 12 weeks after the end of virus administration (if the patient still has unplanned radiological follow-up, the observation of tumor response period continues). Changes in clinical disease status and steroid use will be considered when assessing changes in tumor size. The size of the tumor in the same patient will be calculated by MRI scan. The percentage of participants whose symptoms improved or stabilized after the end of the injection was also pooled using a 95% confidence interval. Time to disease progression, KPS or LPS score, and survival can also be assessed using Kaplan-Meier analysis.

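### 6-month PFS, median PFS and time to progression are planned, but nothing ascertains progression on a schedule after week 12, so these estimates are unreliable in either direction

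*Protocol*

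**What the plan says.** **Endpoints.** Section 6.2 commits to three progression measures: "Time to disease progression, 6-month progression-free survival, median progression-free survival, 12-month overall survival (OS12), and median overall survival will also be determined". Section 10.1 lists time to progression among the secondary endpoints ("Tumor response based on tumor size change on continuous MRI scans after injection, time to progression, viral activity based on sample analysis"); PFS6 and median PFS appear only in 6.2.

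**Imaging.** Section 4.7 schedules MRI at baseline, within 3 days of injection, at day 28, at week 8, and last at "Visit 3 (12±1 weeks after Ad-TD-nsIL12 injection"). It then says: "After the final planned MRI is completed (Visti 3), the study procedure will be completed". An MRI may be requested at any time, but no trigger or interval is set.

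**After week 12.** Section 4.4 says "After 3 months, follow-up visits can be performed by phone, images and blood tests results can be sent by email". Section 4.5 sets "Remote follow-up contact: (6 months ± 1 month, 12 months ± 1 month, 18 months ± 1 month, 24 months ± 1 month"). The items listed for these contacts are survival, quality of life, adverse events with concomitant medication, and steroid use. Progression status is not among them. On imaging, the section says only: "If any imaging tests are performed, radiological information is collected and analyzed".

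**Analysis.** Section 10.4 says: "Time to disease progression, KPS or LPS score, and survival can also be assessed using Kaplan-Meier analysis". It also takes clinical status and steroid use into account when judging tumour size, and lets unplanned scans extend the response observation.

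**The concern.** PFS6 is a landmark at about 26 weeks, yet the last planned tumour assessment is at about 12 weeks. Between them, progression enters the data only if someone orders a scan or happens to report it, often from another hospital. An analysis plan can choose an estimator, but it cannot recover a progression status that the contact schedule never asks for.

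Two related weaknesses sit in section 10.4. Time to progression is named separately from PFS and from survival, so it is open whether a death without documented progression counts. With median survival below one year (section 2.1), such deaths will not be rare after week 12. And KPS or LPS is a repeated score with no event time, so Kaplan-Meier cannot be applied to it until an event is defined.

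At stake is the use that section 10.1 gives these endpoints: reference trends for a later phase II efficacy study.

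**Working it through.** **1. The unobserved interval.** Six months = 6 × 30.44 / 7 = 26.1 weeks. Less 12 weeks, this leaves about 14 weeks with no scheduled assessment before the landmark. Using the stated windows (±1 week, ±1 month), the gap runs from 21.7 − 13 = 8.7 weeks to 30.4 − 11 = 19.4 weeks.

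**2. Inputs.** The protocol gives scan times and a background median survival below one year, but no PFS figure. The following are assumptions: exponential time to progression with median 5, 7 or 9 months, and exponential survival after progression with median 2 or 4 months.

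**3. Worst case: no scan and no clinical detection after week 12, death counted as an event.** Let a = ln2 / (median time to progression), b = ln2 / (median post-progression survival), and c = 84 / 30.44 = 2.76 months. True PFS6 is e^(−6a). A child who progresses between c and 6 months but is still alive at 6 months is wrongly counted as progression-free. That excess is

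excess = a · e^(−6b) · [e^(6(b−a)) − e^(c(b−a))] / (b − a).

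Example, medians 5 and 4: a = 0.1386, b = 0.1733, b − a = 0.03466. Excess = 0.1386 × 0.3536 × (1.2311 − 1.1004) / 0.03466 = 0.185.

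| Median to progression / after it (months) | True PFS6 | Excess | Observed PFS6 |
|---|---|---|---|
| 5 / 2 | 0.435 | 0.142 | 0.578 |
| 5 / 4 | 0.435 | 0.185 | 0.620 |
| 7 / 2 | 0.552 | 0.122 | 0.674 |
| 7 / 4 | 0.552 | 0.157 | 0.709 |
| 9 / 2 | 0.630 | 0.105 | 0.735 |
| 9 / 4 | 0.630 | 0.135 | 0.765 |

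The overstatement is 10 to 19 points. A simulation of 400,000 patients per setting gives the same values within simulation error.

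**4. Less extreme cases.** These come from a simulation of 200,000 patients with true median 6 months (true PFS6 0.50) and post-progression median 4 months.

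| How later progression is found | Children without detected progression | PFS6 | Median PFS (months) |
|---|---|---|---|
| All found at once | Free to last contact | 0.50 | 6.0 |
| All found, mean delay 1 month | Free to last contact | 0.55 | 6.9 |
| All found, mean delay 2 months | Free to last contact | 0.585 | 7.5 |
| All found, mean delay 3 months | Free to last contact | 0.61 | 8.0 |
| Never found; death only | Free to last contact | 0.67 | 10.8 |
| All found at once | Censored at week-12 MRI, data cut at 24 months | 0.48 | 5.7 |
| All found at once | Censored at week-12 MRI, data cut at 12 months | 0.38 | 4.8 |
| All found, mean delay 2 months | Censored at week-12 MRI, data cut at 12 months | 0.49 | 5.9 |

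The same true PFS6 of 0.50 can read anywhere from 0.38 to 0.67. The low values arise because children who progress contribute events, while those who stay well are censored at week 12 and leave the risk set; that censoring is informative. The two errors can also nearly cancel, as in the last row.

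**5. Scale against sampling error.** At a true proportion of 0.50, the standard error is √(0.25/9) = 0.17 with 9 children and √(0.25/18) = 0.12 with 18. The worst-case bias is of that order. Each child of unknown status at 6 months widens the best-to-worst range of a simple proportion by 1/9 = 11 points or 1/18 = 5.6 points.

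**The case against.** A reader might infer that all three measures must be biased upward. The documents do not support that. They fix neither what triggers a later scan nor how unscanned children are censored, and step 4 shows upward bias, no bias and downward bias under different choices.

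A reader might also assume that Kaplan-Meier time to progression censors deaths; on that rule the 6-month figure would reach 70 to 83% under the assumptions of step 2. The protocol states no such rule, and event and censoring rules may stand in an analysis plan that is not shown, so that figure is not a finding. By the usual definition of PFS, death is an event, so the question touches time to progression only.

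The worst case is also harsher than the text suggests. Images may be emailed, investigators contact the treating hospital (section 4.3), an MRI can be requested at any time, clinical status counts in the assessment, and steroid use and adverse events are collected at month 6. Section 4.5 sets different follow-up for children with and without progression, which presupposes that later progression becomes known. If it is found and dated promptly, the bias in PFS6 is small. If the true median were under about 12 weeks, median PFS would rest on scheduled scans and be little affected.

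Finally, the permissive wording of section 10.4 can be read as time to a fall in KPS or LPS. That is a fair reading, but no fall is defined there.

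All this limits direction and size. It does not remove the gap: progression status and its date are not listed items at any contact after week 12.

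**Conclusion.** The concern holds in a limited form. Three progression measures are planned, but the protocol stops scheduled assessment about 14 weeks before the 6-month landmark and does not ask for progression status at that contact. The estimates are therefore unreliable. They are probably overstated if unscanned children count as progression-free, by about 10 to 19 points of PFS6 in the worst case; they are possibly understated if scans follow symptoms and other children are censored at their last MRI. These sizes rest on assumed exponential times and assumed medians, not on figures in the protocol.

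The consequence is modest. There are 9 to 18 children, the secondary endpoints are declared to be reference trends only, and the primary endpoint, 12-month survival and median survival are untouched. The change is still worth making because the missing status may be impossible to reconstruct later.

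**What to change.** - **Section 4.5:** at the 6-month and later contacts, record progression status (clinical or radiological), its date, and the date and result of the last MRI.
- **Sections 10.1 and 10.4:** make PFS, with death as an event, the main progression measure. If time to progression is kept, do not treat death without documented progression as non-informative censoring.
- **Censoring:** censor at the last contact at which clinical or radiological progression status was established, not simply at the last MRI, since the latter can itself bias PFS6 downward.
- **PFS6:** report it with best- and worst-case bounds for children whose status at 6±1 months is unknown.
- **Section 10.4:** replace Kaplan-Meier of the KPS or LPS score with scores by visit, or with time to a pre-stated fall.

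**Cost:** protocol, case report form and analysis wording, and a few more items per contact; no extra scan. PFS6 will be shown with bounds and may look less favourable. Irregular scanning itself remains, so some delay in dating progression will persist.
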